##### **3.2.2. Secondary Endpoints**

The secondary endpoints of this study are as follows:

1. Change in Hgb from Baseline at Week 48
2. Time from randomization to first increase from Baseline Hgb of at least 0.5 g/dL
3. Change in transferrin saturation (TSAT) from Baseline at Weeks 24 and 48
4. Change in ferritin from Baseline at Weeks 24 and 48
5. Change in serum phosphate from Baseline at Weeks 24 and 48
6. Change in estimated glomerular filtration rate (eGFR) from Baseline at Weeks 24 and 48
7. Change in bicarbonate from baseline at Weeks 24 and 48
8. Change in intact parathyroid (iPTH) from baseline at Weeks 24 and 48
9. Change in C-terminal fibroblast growth factor 23 (FGF 23) from baseline at Weeks 24 and 48
10. Change in intact fibroblast growth factor from baseline at Weeks 24 and 48
11. Change in score for Work Productivity and Activity Impairment (WPAI) questionnaire adapted for anemia associated with chronic kidney disease from Baseline at Weeks 24 and 48 (A copy of the questionnaire is in Section 11.1.)
12. Change in score on the FACIT Fatigue Scale (Version 4) from Baseline at Weeks 24 and 48 (A copy of the questionnaire is in Section 11.3.)
13. Number of hospitalizations and duration (days)

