### 6.3.5. Per Protocol Analysis Set

The Per Protocol (PP) Analysis Set will include all subjects in the FAS who have no major protocol deviations that affect the validity of the efficacy measurements (see section 7.2) and have not received additional treatment that affect the validity of the efficacy measurements.

The following criteria exclude a subject from the PP Analysis Set:

- Receive red blood cell transfusions within 4 weeks prior to screening or at any time during the study.
- Receive ESAs (permitted or non-permitted) within 4 weeks prior to screening or at any time during the study.
- Receive IV Iron within 4 weeks prior to screening or at any time during the study.
- Pregnancy during screening or at any time during the study.
- Overall drug compliance < 50% i.e., from randomization to the Week 48 Visit date or to Early Termination date (whichever is earlier). (See section 7.4.1 Compliance Calculation)
- Major violations of eligibility criteria as determined by review prior to database lock.

The PP analysis set will be used for the 24-Week and Final analyses.

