## 8. EFFICACY

### 8.1. General Considerations

Efficacy analyses will be based on the PP Analysis Set data for the 24-Week and Final analyses (mPP Analysis Set for 24-Week analysis snapshot). Additionally, efficacy of the study drug in the FAS subgroup of subject who received rescue therapy under the conditions specified in section 9.2.2 of protocol will be assessed.

Table 3 lists the efficacy endpoints of special focus for the 24-Week Analysis snapshot and the 24-Week and Final Analyses showing the analysis method and analysis set to be used in assessing them. See section 8.2 for any special conditions to be explored for implementation of the analysis method or alternatives that will necessitate implementation of an alternative method.

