**Table 3: Analysis Method and Analysis Set for Special Focus Efficacy Endpoints**

Efficacy Parameter	24-Week Analysis (Study Period: Dose Titration Period)	Final Analysis (Study Period: Entire Study)	Analysis Method	Analysis Set
Hgb	Change from Baseline to Week 24*	Change from Baseline to Week 48	MMRM	PP 
Hgb	Change from Baseline at Week 24	Change from Baseline at Week 48	ANCOVA	PP  Completers
Hgb	Time from Randomization to First Increase from Baseline Hgb >= 0.5 g/dL	Not Applicable	Kaplan-Meier	PP 
TSAT, ferritin, phosphate, bicarbonate, eGFR	Change from Baseline to Week 24	Change from Baseline to Week 48	MMRM	PP 
PTH, c-terminal and intact FGF-23	Change from Baseline to Week 24	Change from Baseline to Week 48	ANCOVA	PP 
FACIT score	Change from baseline at Week 24	Change from Baseline to Week 48	Descriptive	PP 
WPAI	Change from Baseline to Week 24	Change from Baseline to Week 48	Descriptive	PP 
Hospitalizations	Number and Duration ( days)	Number and Duration ( days)	Descriptive	PP 

Hgb, TSAT, ferritin, phosphate	Change from Baseline to Week 24	Change from Baseline to Week 48  Change from Baseline to Week 24	MMRM	FAS subjects who received permitted ESA Rescue Therapy
Hgb, TSAT, ferritin, phosphate		Change from Baseline to Week 48  Change from Baseline to Week 24	MMRM	PP Dosing sequence groups

\* Hgb change from baseline to Week 24 is the primary endpoint.

The analysis set used will either be the modified PP Analysis Set (24-Week Analysis snapshot) or PP Analysis Set (24-Week and Final Analysis).

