where the change from Baseline at Week 24 results and the change from Baseline at Week 48 results will be presented in tables for the 24-Week analysis and the Final analysis, respectively.

Descriptive statistics will also be provided for the number of hospitalizations and duration of hospital stay in days during the Dose Titration Period and the entire study for the 24-Week Analysis and Final Analysis, respectively.

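### Number and duration of hospitalizations are summarised only in the Per Protocol set, so the plan has no count or days of admissions for all treated subjects

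*SAP*

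**What the plan says.** Hospitalization count and duration is a named secondary efficacy endpoint in Protocol 6.1.2 and SAP 3.2.2. SAP 8.3 plans the summary: "Descriptive statistics will also be provided for the number of hospitalizations and duration of hospital stay in days during the Dose Titration Period", with a matching summary over the entire study for the Final Analysis. That sentence names no analysis set.

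The set is fixed elsewhere. SAP 8.1 says "Efficacy analyses will be based on the PP Analysis Set data for the 24-Week and Final analyses". Table 3 lists hospitalizations as descriptive, with a footnote reading "The analysis set used will either be the modified PP Analysis Set (24-Week Analysis snapshot) or PP Analysis Set (24-Week and Final Analysis".

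SAP 6.3.5 removes a subject from PP for any of these, among others:
- transfusion, worded as "Receive red blood cell transfusions within 4 weeks prior to screening or at any time during the study"
- an ESA over that same span, whether its use was allowed or not
- intravenous iron, likewise
- overall compliance below 50%, measured to Week 48 or early termination.

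Pregnancy and major eligibility violations also exclude.

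Protocol 15.7 called for every efficacy analysis in both FAS and PP, with PP primary and FAS as the check on the effect of exclusions. SAP 9.6 withdraws the FAS analyses, except in the permitted-ESA subgroup, on the ground that excluded subjects carry confounders of efficacy.

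**The concern.** Transfusion, ESA and IV iron act on hemoglobin and iron indices, so there is an argument for setting those subjects aside when estimating change in hemoglobin. The argument does not carry over to admissions. An admission is a countable event whether or not the subject was later given an ESA, and the SAP gives no reason why such a count would be invalid.

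The exclusion also works on whole subjects and, apart from its pre-screening part, on events after randomization. SAP section 5 runs both main analyses at the end of the study, and the PP rule looks at the full study. An ESA given at Week 40 would therefore remove a Week 6 admission even from the 24-week table. What is at stake is a secondary endpoint whose only planned summary describes a subset chosen partly by how subjects fared, with the protocol's own sensitivity analysis withdrawn.

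**Working it through.** **1. Is the endpoint restored anywhere else?**
- SAP 8.4 uses the FAS for the permitted-ESA subgroup, but only for hemoglobin, TSAT, ferritin and phosphorus.
- SAP 7.3 lists hospitalizations as a baseline characteristic for the PP and Safety sets. That is not the on-study endpoint.
- SAP section 9 defines safety data as adverse events, vital signs and laboratory values. Sections 9.1 and 9.2.3 count treated subjects with serious events, the latter by system organ class and preferred term. Neither gives number of admissions or days.
- Protocol 13.2.1.2 makes event-driven admissions serious adverse events, but leaves some admissions (elective, social) outside serious-event reporting.

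So counts and days exist only in PP (or modified PP for the snapshot).

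**2. Can the size be computed?** The plan states no hospitalization figure to reproduce. It gives no admission rate, and SAP 4.3.1 merges dropout with PP exclusion in one 30% allowance. That 30% is thus only an upper limit for the planned share excluded. What follows is illustration under assumptions.

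Let f be the share of treated subjects excluded from PP, and R the mean admissions per excluded subject divided by the mean per included subject. Then

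PP mean / all-treated mean = 1 / (1 − f + f × R).

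Percentage by which PP understates the all-treated mean:

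| f | R = 1 | R = 2 | R = 3 | R = 4 |
|---|---|---|---|---|
| 5% | 0 | 4.8 | 9.1 | 13.0 |
| 10% | 0 | 9.1 | 16.7 | 23.1 |
| 20% | 0 | 16.7 | 28.6 | 37.5 |
| 30% | 0 | 23.1 | 37.5 | 47.4 |

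Example: f = 10%, R = 2 gives 1 / (0.90 + 0.20) = 0.909, so 9.1% low.

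**3. Effect of early exit.** Protocol 9.2.1 requires a subject given IV iron or a transfusion to stop drug and leave the study. R is then the rate ratio times the follow-up ratio. Assume half the follow-up, with 10 or 20 of 190 treated subjects excluded:
- Rate ratio 2: R = 2 × 0.5 = 1, no difference in raw counts.
- Rate ratio 3: R = 1.5. With 10 excluded, (10 × 1.5 + 180) / 190 = 1.026, PP 2.6% low. With 20 excluded, (20 × 1.5 + 170) / 190 = 1.053, PP 5.0% low.
- Full follow-up, for contrast: 10 excluded at rate ratio 2 gives (20 + 180) / 190 = 1.053, 5% low; 20 at rate ratio 3 gives (60 + 170) / 190 = 1.211, 17% low.
- Equal rates: R = 0.5. At f = 10%, 1 / (0.90 + 0.05) = 1.053, so the PP raw mean would be 5.3% too high.

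Raw counts can also hide a real difference in rates. With f = 10%, half follow-up and rate ratio 2, raw means agree, but the all-treated rate relative to PP is (0.90 + 0.10 × 0.5 × 2) / (0.90 + 0.10 × 0.5) = 1.00 / 0.95 = 1.053, so the PP rate is 5.0% low.

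**The case against.** The other side has four good points.

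- **The protocol itself treats hospitalizations as an efficacy endpoint, makes PP primary and asks only for description.** The SAP discloses that it dropped the FAS. This stands, and it limits the issue to the missing second analysis. Disclosure does not supply a reason that fits this endpoint.
- **The events are still reported.** Admissions that are serious adverse events enter the all-treated tables and the subject listings. A reader might infer that excluded subjects' admissions vanish from the report; they do not. Only the counts-and-days summary loses them.
- **The link between exclusion and illness is partly inference.** A reader might conclude that PP leaves out the sickest subjects. Permitted ESA rescue does require two consecutive hemoglobin values below 8.0 g/dL (Protocol 9.2.2), which supports a link to severe anemia. But nothing in that rule involves admission, and Protocol 5.1 describes IV iron as office or infusion-center care. Pregnancy and eligibility exclusions need not mark illness, and an ordinary hospital stay would not pull 48-week compliance below 50%.
- **Early exit cuts the follow-up of transfused and IV-iron subjects.** As shown above, this can shrink the raw-count difference to nothing or reverse it. It applies less to ESA-rescued subjects, who may remain in the study. It argues for reporting by subject-time, not for leaving these subjects out.

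**Conclusion.** The point holds as one of scope. The plan summarises number and duration of hospitalizations only in a set that removes whole subjects partly for post-randomization events. The stated reason for abandoning the FAS does not cover this endpoint, and nothing else supplies counts and days for all treated subjects.

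Understatement is likely if excluded subjects are admitted more often, but a reader should not infer that the result is certainly biased low in both groups, or by any particular amount. The documents contain neither an admission rate nor a separate PP-exclusion rate. Under full follow-up the illustrated understatement runs from 0% (R = 1) to 47% (f = 30%, R = 4), the top resting on the upper limit for f. With half follow-up and 10 to 20 of 190 excluded, it is about 0% to 5% for rate ratios of 2 to 3. The endpoint is secondary and descriptive, so the primary hemoglobin analysis is unaffected.

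**What to change.** In SAP Table 3 and section 8.3, name the Safety Analysis Set for number and duration of hospitalizations, by starting dose and for both groups combined. The FAS, as the protocol planned, would also serve. Report admissions and hospital days per subject-time alongside the raw counts, because early exits make raw counts hard to compare. Keep PP as a supporting row, and record the change in SAP 9.6.

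The cost is one table cell, a sentence or two of text and one extra output. No new data are needed, since SAP 4.5 has hospitalizations assessed at each visit. The downside is that the all-treated figure may be less favourable.

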Prohibited Therapies

The use of IV iron, blood transfusions, phosphate binders other than KRX-0502, oral iron therapy other than KRX-0502 as treatment for iron deficiency (multivitamins containing iron are permitted), commercial ferric citrate, aluminum-containing therapies, or investigational drugs other than KRX-0502 will not be permitted at any time during the study (beginning with the Screening visit).

The use of ESA is also not permitted during the study, except if used in the specifically defined scenario of ESA rescue therapy (see [Section 9.2.2](#))

If a subject receives a dose of IV iron or a blood transfusion, the subject will immediately discontinue KRX-0502, complete the Early Termination visit assessments, and exit the study. Any subject who is to receive or has received any prohibited medications other than IV iron or a blood transfusion should be discussed with the Medical Monitor as soon as possible to determine the most appropriate course of action (see [Section 9.2.1](#) and [Section 9.2.2](#)).

Duration of treatment:

24-week Dose Titration Period followed by a 24-week Dose Maintenance Period (48 weeks total)

Reference therapy, dosage and mode of administration:

Not applicable

Criteria for evaluation:**Efficacy:**Primary endpoint:

The primary efficacy endpoint is the change in Hgb from Baseline at Week 24.

Secondary endpoints:

Secondary endpoints are as follows:

1. Change in Hgb from Baseline at Week 48
2. Change in TSAT from Baseline at Weeks 24 and 48
3. Change in ferritin from Baseline at Weeks 24 and 48
4. Change in serum phosphate from Baseline at Weeks 24 and 48
5. Change in scores for Work Productivity and Activity Impairment (WPAI) questionnaire from Baseline at Weeks 24 and 48
6. Change in score of Functional Assessment of Chronic Illness Therapy (FACIT) Fatigue Scale from Baseline at Weeks 24 and 48
7. Number of hospitalizations and duration (days)

Safety:

Safety evaluations will be based on the following:

- Incidence, seriousness, intensity, duration, and type of AEs
- Clinically significant changes in the subject's vital signs and laboratory test results

Statistical methods:**Efficacy:**

The change in Hgb from Baseline is the primary endpoint of interest. Ninety-five percent confidence intervals (CI) will be constructed for change from Baseline at Week 24 and change from Baseline at Week 48 based on the entire sample and by randomized dose groups. No imputation will be performed for these analyses.

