8.3. Subject Withdrawal Criteria

8.3.1. Discontinuation From Study Drug

Discontinuation from study drug is defined as a permanent termination of treatment with KRX-0502. Subjects may be discontinued from the study drug at any time for any of the following reasons:

- Adverse event
- Lack of efficacy (see [Section 9.2.2](#))
- Pregnancy
- Withdrawal by subject
- Other

If at any time during the course of the study, in the opinion of the Investigator, the subject may no longer safely participate due to a change in medical status (eg, experiences an AE, becomes pregnant), the subject must be discontinued from the study drug.

Whenever study drug is discontinued prematurely, Keryx and the Medical Monitor must be notified. The subject should return for the ET visit and exit the study.

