15.7.2. Secondary Efficacy Analyses

A Mixed Model Repeated Measures (MMRM) model will be fitted to the change from Baseline Hgb incorporating all visits at which Hgb is measured for each subject. Baseline Hgb and randomized dose group will be applied as fixed effects, as will time (in weeks) and time-by-dose group interaction. An unstructured within-subject covariance structure will be assumed.

The MMRM model is one approach to obtain treatment effect estimates in the presence of missing data. As a sensitivity analysis to MMRM fitted to observed-case data, missing Hgb data will be imputed using multiple imputation (MI) methods described in [Section 15.10.3](#).

TSAT, ferritin, and serum phosphorus will be analyzed in a manner similar to the primary endpoint stated above.

Changes in scores for the WPAI questionnaire and the FACIT Fatigue Scale, and frequency of hospitalizations and hospital days will be analyzed descriptively.

Efficacy analyses will be repeated, substituting the dosing sequence groups for the randomized dose groups if appropriate, based on the distribution in the 4 dosing sequence groups (3-3, 3-6, 4-4, and 4-6 tablets/day). The dosing sequence groups will be determined based on actual doses received by each subject.

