### 4.3. Sample Size Considerations

#### 4.3.1. Sample Size Justifications

Because this is an open-label Phase 4 study designed to estimate within-group changes from Baseline and describe time trends of iron parameters in subgroups of subjects, it is appropriate to conduct a precision-based sample size estimation as opposed to a power-based calculation. The primary endpoint of interest is change in Hgb from Baseline at Week 24. The standard deviation

(SD) for that endpoint is estimated as 0.9 g/dL based on the Week 16 data in a prior Phase 3 study in a similar population (Keryx Study KRX-0502-306).

Assuming a population SD of 0.9 g/dL, with a sample size of 140 subjects, the 95% confidence intervals (CIs) for mean change in Hgb from Baseline to Week 24 can be estimated, allowing for a CI half-width of 0.149 g/dL.

It is assumed that 30% of the subjects in this study will drop out or be otherwise excluded from the PP population. Hence, 200 subjects will be randomized to ensure that there will be sufficient subjects at the end of the study for the longitudinal analyses (i.e., 70 evaluable subjects in each randomized treatment group). Based on prior clinical trial experience, it is estimated that half of the subjects will stay on their starting dose, and the other half will increase their dose after 12 weeks of treatment. Hence, it is expected that the 4 dosing sequence groups that will arise will have approximately equal numbers of subjects (i.e., 35 subjects are expected in each of the four dosing sequence groups (3-3, 3-6, 4-4, and 4-6 tablets/day).

The proposed sample size and the sizes of the subgroups of interest are deemed sufficient for the analyses proposed below including the longitudinal analyses.

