## 5.2. Final Analysis

The final analysis will be based on the full set of cleaned data for all visits up to and including the Week 48 visit (i.e. it will cover the Dose Titration Period and the Dose Maintenance Period).

Data for this analysis are the data for those subjects who completed the Week 48 visit or had Early Termination from the study prior to Week 48.

Some tables, listings and figures produced for the final analysis will display statistics for both the Dose Titration and the Dose Maintenance treatment periods.

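### Hospitalisation counts and days are summarised without follow-up time, so early exits pull them below the full 24- or 48-week burden

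*SAP*

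**What the plan says.** The number and duration of hospitalisations form a named secondary endpoint in both documents (protocol 6.1.2, SAP 3.2.2). The planned analysis is short.

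- SAP 8.3: "Descriptive statistics will also be provided for the number of hospitalizations and duration of hospital stay in days", for the Dose Titration Period and for the entire study. SAP Table 3 gives the method as descriptive and the set as PP (modified PP for the 24-week snapshot).
- Protocol 15.7.2 agrees: "frequency of hospitalizations and hospital days will be analyzed descriptively".
- SAP 6.2 defines descriptive statistics for continuous data as n, mean, SD, median, quartiles, minimum and maximum.

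Other sections determine how long each subject is observed and who is counted.

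- Protocol 8.3.1, on premature stopping of study drug: "The subject should return for the ET visit and exit the study".
- Protocol 8.3.2 lists chronic dialysis, transplantation and death among the reasons for leaving.
- SAP 5.2 bases the final analysis on "those subjects who completed the Week 48 visit or had Early Termination from the study prior to Week 48".
- SAP 6.3.5 does not make completion a PP criterion, and it measures compliance up to Week 48 or early termination (ET), whichever comes first.
- SAP 6.6.1 rules out imputation of missing efficacy data.
- SAP 4.3.1 on losses: "It is assumed that 30% of the subjects in this study will drop out or be otherwise excluded from the PP population".

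No section gives a rate, an offset or a follow-up summary for this endpoint.

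**The concern.** A count of admissions or a total of hospital days can only grow with time. If one subject is watched for 8 weeks and another for 48, and neither is admitted, the planned summary treats the two zeros as equal evidence. Recording takes place at scheduled visits and the ET visit, so exit ends capture for this endpoint, and the subject may still sit in the PP mean with a truncated total.

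Two things are at stake. A reader will take the entire-study figures as the burden over 48 weeks, when they are the burden over whatever time was observed. A reader will also set the two starting-dose columns side by side, and any difference in retention would then look like a difference in hospitalisation. Some listed exit reasons reflect worsening illness, so the missing time may be the time with most admissions.

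The SAP does allow for unequal follow-up elsewhere. It censors the time to haemoglobin increase at discontinuation (8.3) and reports subject-months of drug exposure in the tolerability table (9.1). It does not link either to hospitalisations.

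**Working it through.** **The plan's own figures.** The documents state no figure for hospitalisations. The stated precision and sample size reproduce: half-width 1.96 × 0.9 / √140 = 0.149 g/dL, and 140 / (1 − 0.30) = 200 randomised.

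**Inputs.** Planned follow-up is 24 weeks (Dose Titration Period) and 48 weeks (entire study). The 30% loss comes from SAP 4.3.1. The documents give no admission rate, exit times or drop-out share, so those below are assumptions.

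**Why 30% is an upper bound.** It covers drop-out and PP exclusion together, and subjects outside the PP set cannot dilute a PP mean. If all 60 of 200 lost subjects were early leavers who stayed in PP, the share would be 60/200 = 30%. If, say, 20 of the 60 were instead excluded from PP, it would be 40/180 = 22%.

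**Shortfall at a constant rate.** Let d be the share of the analysed set leaving early and f the average fraction of the period they complete. The mean count relative to full follow-up is (1 − d) + d·f, so the shortfall is d·(1 − f).

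| d | f = 25% | f = 50% | f = 75% |
|---|---|---|---|
| 10% | 7.5% | 5.0% | 2.5% |
| 20% | 15.0% | 10.0% | 5.0% |
| 30% | 22.5% | 15.0% | 7.5% |

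For d = 30% and f = 50%, mean follow-up is 0.7 × 48 + 0.3 × 24 = 40.8 weeks, and 40.8/48 = 0.85. The percentages are the same for the 24-week period at the same d and f.

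**Between groups.** Take equal true rates and exits halfway. With 20% leaving one group and 40% the other, the relative means are 0.90 and 0.80, a ratio of 0.889: an apparent 11% difference from follow-up alone. With 25% and 35% the ratio is 0.825/0.875 = 0.943. Both splits are assumed, and both average 30%, the upper bound.

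**What a person-time rate repairs.** Set the stayers' rate to 1 per 48 weeks, with d = 30% and f = 50%.

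- Leavers at the same rate: observed count 0.85 over 0.85 of full time gives a rate of 1.00, so the shortfall disappears.
- Leavers at twice the rate: the true mean is 0.7 + 0.3 × 2 = 1.30 and the observed mean is 0.7 + 0.3 × 0.5 × 2 = 1.00. The raw count is 23.1% low. The pooled rate, 1.00/0.85 = 1.176, is 9.5% low.
- Leavers at three times the rate: the true mean is 1.60 and the observed mean 1.15, so the raw count is 28.1% low. The pooled rate, 1.15/0.85 = 1.353, is 15.4% low.

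**The case against.** The strongest reply is that the size is unknown and may be small. IV iron or transfusion forces exit (protocol 9.2.1) and also removes the subject from PP, so those leavers never enter the mean. ESA use and compliance below 50% exclude subjects too. The wording of SAP 4.3.1 can even be read as placing drop-outs outside PP, although the criteria in SAP 6.3.5 do not do so. Eligibility also screens out planned dialysis, transplantation and long admissions within 6 months. All of this stands, and it is why the low end of the range matters as much as the high end.

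Second, the study estimates within-group change, and hospitalisations carry no test. A reader might infer that the plan makes an invalid comparison between periods, or that retention will differ between the starting doses. The documents support neither. The titration-period and entire-study summaries plainly differ in length and are not contrasted, and nothing predicts unequal retention. The concern about groups is conditional.

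Third, some context is reported elsewhere: disposition by group (SAP 7.1) and duration of drug exposure (SAP 9.3). These show that follow-up varies, but they do not give time on study in the PP set, so they soften the gap without closing it. Serious events are also collected for 28 days after the study or treatment ends (protocol 13.2.2), but whether such admissions count here is not stated.

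Last, the per-subject reading is inferred from SAP 6.2, and the table shells named in SAP 11.5 are a separate document. A rate row there cannot be ruled out, but the SAP text should then say so.

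**Conclusion.** The concern holds as a minor one. As written, the hospitalisation summary ignores time observed and understates the burden over a full 24 or 48 weeks whenever early leavers are in the PP set. The direction is certain, because truncation cannot raise a cumulative total. The size is not: 2.5% to 22.5% is an illustration for 10% to 30% leaving after 25% to 75% of the period at a constant rate.

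A reader might take 15% or 22.5% as the expected bias. The documents do not support that, because both figures shown for 30% leaving sit at the upper bound of the loss and rest on assumed exit times. Nor should a reader infer that a person-time rate cures the problem. It removes the shortfall only if the rate is constant and unrelated to exit, and it does nothing about the PP exclusion of subjects given transfusion, IV iron or ESA. The primary endpoint and the sample size are unaffected.

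**What to change.** Keep the planned table and add to SAP 8.3, by starting dose and overall, for the Dose Titration Period and the entire study:

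- total hospitalisations and total hospital days, each divided by subject-years of time on study;
- time on study defined as randomisation to the Week 24 visit (or Week 48 visit for the entire study) or ET, whichever is earlier, with events counted over the same interval. The drug exposure in SAP 9.3.1 is unsuitable because it subtracts prescribed interruptions;
- mean follow-up by group;
- a 95% CI for the admission rate that allows for repeat admissions within a subject, for example from a negative binomial model or a robust variance. A simple Poisson interval would tend to be too narrow.

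State beside the table that the rate reduces, but does not remove, bias from illness-related exit. The cost is one extra derivation and a few table rows. The SAP already relies on visit and ET dates for its compliance rules, so no new data are needed.
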